5.2.2. Patient Disposition

Summary of analysis population for each treatment group and combined groups will be presented. A listing of the primary reason for patient discontinuation will be presented for all randomized patients. Summary of patients disposition of study and study treatment will be conducted for the all randomized populations, and its frequency counts and percentages will be presented for each treatment group and combined groups. Summary of number of patients entered, number of randomized patients, and number of patients discontinued study during treatment period will be summarized by site.

A listing of subjects with treatment assignment and stratification categories will be created for all randomized patients.

A listing of subjects with visit date of each visit will be presented. A second listing of dates with first patient visit (visit 1), randomization (visit 2), last treatment visit (visit 18 or ED visit) and safety follow-up visit (V801).

A listing of subjects indicating its population flag and assigned treatment group will be provided for all patients entered.

A listing of subjects discontinue from study or study treatment due to COVID-19 will be provided.

5.2.3. Patient Characteristics

The patient's age, sex, weight, height, BMI, or other demographic characteristics will be recorded.

Demographic and baseline characteristics will be summarized by treatment group for the FAS and PP populations. For continuous measures, summary statistics will include sample size, mean, median, maximum, minimum and SDs. The treatment groups will be compared using a 2-sample *t* test. For categorical measures, summary statistics will include sample size, frequency, and percentage. Analysis will use Fisher's exact test. To avoid computational problems, a maximum computation time of five minutes will be programmed into the analysis for Fisher's exact test. If it does not converge in that time, the Pearson's Chi-square test will be utilized.

5.2.4. Concomitant Therapy

Concomitant medications, including previous therapy for diabetes, will be summarized by different categories and treatment group using the FAS population. All concomitant therapies

that originally mapped using the WHODRUG dictionary in the Clintrial database will be reported using preferred term.

Oral antihyperglycemic medications (OAM) will be classified into classes of drugs [alpha glucosidase inhibitors, dipeptidyl peptidases (DPP) IV inhibitors, meglitinide, metformin, sulfonylurea, Sodium-glucose co-transporter 2 (SGLT2) inhibitors, and thiazolidinedione (TZD)]. Summary tables will be provided by treatment showing the number of OAMs and the particular combination classes of OAMs for patients with 2 OAMs, 3 OAMs, and > 3 OAMs.

5.2.5. Treatment Compliance

No specific study data will be collected for analysis of treatment compliance.

5.2.6. Protocol Violations

A comprehensive listing of patients with important protocol deviations (IPD) or protocol violations that could potentially impact data interpretation, data integrity and patient safety across the I4L-GH-ABET study will be provided. A listing of protocol deviations (PD) due to coronavirus disease 2019 (COVID-19) will be provided. A summary of IPD and IPD due to COVID-19 by treatment group and overall will also be provided.

Important protocol deviations will be identified from the clinical database and from site monitoring. Categories of IPDs will be documented in the “ABET trial issue management plan” that will contain detailed criteria used to identify IPDs. Detailed programming specifications for IPDs (ADaM PD dataset specification) will be stored in CLUWE prior to database lock.

5.2.7. Primary Efficacy Outcome and Methodology

The primary efficacy outcome will be the change in HbA_{1c} level from baseline to 24 weeks. The primary analysis will be a likelihood-based, MMRM approach, treating the data as missing at random (MAR) for the FAS population. The MMRM model will evaluate the change from baseline to each post-baseline visit in HbA_{1c} level as the dependent variable with treatment (LY2963016, Lantus®), entry use of insulin scretagogue (SU, meglitinide, neither), visit, and interaction between visit and treatment as fixed effects; the baseline value of HbA_{1c} as a covariate; and a random effect for patient. An unstructured covariance structure will be used to model the within-patient errors. Significance tests will be based on LS means and Type III tests. If this analysis fails to converge, the following covariance structures will be tested in order:

- Toeplitz with heterogeneity
- autoregressive with heterogeneity
- compound symmetry with heterogeneous variances
- Toeplitz
- autoregressive
- compound symmetry without heterogeneous variances

The first covariance structure that converges will be used. The Kenward-Roger approximation will be used to estimate denominator degrees of freedom.

The primary treatment comparison is to compare LY2963016 versus Lantus® at the NIM of +0.4%. If the upper limit of the 95% CI on the change from baseline to 24-week endpoint HbA_{1c} for LY2963016 versus Lantus® is below +0.4%, then LY2963016 will be declared noninferior to Lantus®. The LSMean and standard error derived from the MMRM model for each treatment will be used to test noninferiority. Type III sums of squares will be used to make the treatment comparisons.

- If the +0.4% NIM is met, a key secondary treatment comparison is to compare Lantus® versus LY2963016 at the NIM of -0.4%. If the lower limit of the 95% CI on the change in HbA_{1c} from baseline to the 24-week endpoint for LY2963016 versus Lantus® is above -0.4%, then Lantus® will be declared noninferior to LY2963016. The LSMean and standard error derived from the MMRM model for each treatment will be used to test noninferiority. This gate-keeping procedure controls the family-wise Type 1 error rate at a 1-sided 0.025 level.
- If LY2963016 is declared noninferior to Lantus® in the primary treatment comparison, and Lantus® is declared noninferior to LY2963016 in this secondary treatment comparison, then LY2963016 will be considered to have equivalent efficacy as Lantus®.

A first secondary analysis of the primary efficacy outcome will use the same MMRM model described above with the PP patient population. Significance tests will be based on LSMeans using the Type III sum of squares, and testing for noninferiority will occur as described above.

A second secondary analysis of the primary efficacy outcome will use an ANCOVA model with FAS population. The ANCOVA model will include treatment and entry use of insulin scretagogue (SU, meglitinide, neither) as fixed effects and the baseline value of HbA_{1c} as covariate. The ANCOVA model will be carried out using the OM option in SAS GLM procedure. If the 24-week HbA_{1c} value is missing, the last post-baseline value will be carried forward and used in the analysis. This creates the 24-week endpoint value for HbA_{1c} using the LOCF methodology. If there are no HbA_{1c} data after the date of randomization, the endpoint will be considered missing and the patient will not be included in the analysis.

The analyses of the primary efficacy outcome will only be conducted for patients with both nonmissing baseline value and at least 1 nonmissing post-baseline value.

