**Figure ABET.7.1. Study design for Clinical Protocol I4L-GH-ABET.**

## 7.2. Discussion of Design and Control

### 7.2.1. Introduction

The present study is a randomized, open-label trial that will compare the efficacy and safety of LY2963016 to Lantus® in patients with T2DM. The study patients will be insulin naïve and on 2 or more OAMs with inadequate glycemic control.

This study is designed to allow comparison of the 2 insulin analogs, with regard to efficacy and safety, when used as a basal insulin therapy in these patient populations. The study design includes the following periods: Screening, Randomization, Treatment Period (composed of a Titration Period and a Maintenance Period), and a Follow-up Period. It is expected that most of the titration will be completed during the Titration Period (Week 0 through Week 12) such that a patient is on a relatively stable basal insulin dose during the Maintenance Period (Weeks 13 through Weeks 24) during which adjustments to insulin dose would be for safety such as hypoglycemia or unacceptable hyperglycemia.

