### **8.3.3. Patient Discontinuation from the Study**

Patients will be discontinued from the study in the following circumstances:

- If any of Exclusion criteria ([14 to 15], [17 to 20], [23], [25], and [27 to 28]) are observed or develop after entry. In this case, the patient may be discontinued from the study at the next visit, or sooner, if patient safety is the rationale for the exclusion criterion
- If there is a lack of efficacy or the need to intensify the patient's treatment (Section 9.5.1) beyond basal insulin dosing, based on investigator discretion that the patient has not had adequate progress in the reduction of HbA1c levels in spite of adequate basal insulin titration and dosing. For example: Based on investigator clinical judgment, a patient may be deemed appropriate to discontinue from the study if he/she is consistently achieving target FBG levels  $\leq 100$  mg/dL (5.6 mmol/L), but HbA1c levels remain above 8.0% on at least 2 consecutive occasions in the absence of any signs of continued improvement. Or, a patient may be deemed appropriate to discontinue from the study if he/she is not achieving target FBG levels  $\leq 100$  mg/dL (5.6 mmol/L) but is experiencing hypoglycemia that would preclude further basal insulin titration
- If the patient is off study medication for more than 14 consecutive days
- If the patient has used short/rapid-acting insulin for glucose control and management of diabetes during an acute illness/injury for more than 14 consecutive days
- If the patient enrolls in any other clinical trial involving an investigational product or enrollment in any other type of medical research judged not to be scientifically or medically compatible with this study
- Investigator Decision
  - if the investigator decides that the patient should be discontinued from the study
  - if the patient, for any reason, requires treatment with another therapeutic agent that has been demonstrated to be effective for treatment of the study indication, discontinuation from the study occurs prior to introduction of the new agent
- Subject Decision
  - if the patient or the patient's designee, for example, parents or legal guardian requests to be withdrawn from the study
- Sponsor Decision

- if Lilly or its designee stops the study or stops the patient's participation in the study for medical, safety, regulatory, or other reasons consistent with applicable laws, regulations, and GCP
- Adverse Event

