### **12.2.6. Primary Efficacy Outcome and Methodology**

The primary efficacy outcome will be the change in HbA1c level from baseline to 24 weeks. The primary analysis will be a likelihood-based, MMRM approach, treating the data as missing at random (MAR) for the FAS population. The MMRM model will evaluate the change from baseline to each post-baseline visit in HbA1c level as the dependent variable with treatment (LY2963016, Lantus®), entry use of insulin scretagogue (SU, meglitinide, neither), visit, and interaction between visit and treatment as fixed effects; the baseline value of HbA1c as a covariate; and a random effect for patient. The MMRM model will be carried out using the observed margins (OM) option in SAS. Using this option weights the levels of the independent or stratification variables according to the observed marginal distribution. This will provide least-squares means (LSMeans) for these outcomes that are more representative of the patient population recruited in this study.

The primary treatment comparison is to compare LY2963016 versus Lantus® at the NIM of +0.4%. If the upper limit of the 95% CI on the change from baseline to 24-week endpoint HbA1c for LY2963016 versus Lantus® is below +0.4%, then LY2963016 will be declared noninferior to Lantus®. The LSMean and standard error derived from the MMRM model for each treatment will be used to test noninferiority. Type III sums of squares will be used to make the treatment comparisons.

- If the +0.4% NIM is met, a key secondary treatment comparison is to compare Lantus® versus LY2963016 at the NIM of -0.4%. If the lower limit of the 95% CI on the change in HbA1c from baseline to the 24-week endpoint for LY2963016 versus Lantus® is above -0.4%, then Lantus® will be declared noninferior to LY2963016. The LSMean and standard error derived from the MMRM model for each treatment will be used to test noninferiority. This gate-keeping procedure controls the family-wise Type 1 error rate at a 1-sided 0.025 level.
- If LY2963016 is declared noninferior to Lantus® in the primary treatment comparison, and Lantus® is declared noninferior to LY2963016 in this secondary treatment comparison, then LY2963016 will be considered to have equivalent efficacy as Lantus®.

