5.2.11.1.2. Assessment of Injection Site Adverse Events.....	14
5.2.11.2. Hypoglycemic Events.....	14
5.2.11.3. Laboratory Measures – Chemistry/Hematology Panel.....	16
5.2.11.4. Laboratory Measures – Insulin Antibodies.....	16
5.2.11.5. Vital Signs.....	18
5.2.11.6. Other Safety Measures.....	19
5.2.12. Subgroup Analyses	20
5.2.13. Interim Analyses	22
5.2.14. Exploratory Analysis.....	22
5.2.15. Required Analyses for the Clinical Trial Registry (CTR).....	22
6. Unblinding Plan	23

7. References	24
8. Appendices	25

Table of Contents

Appendix		Page
Appendix 1.	List of Allergic Reaction Terms.....	26
Appendix 2.	Estimation of Creatinine Clearance Using the Cockcroft-Gault and MDRD for the Approximation of Glomerular Filtration Rate (GFR).....	28

3. Revision History

SAP Version 1 was approved prior to the First Randomized Patient.

Version 2 of the SAP will be approved prior to the first unblinding of the clinical team and prior to the database lock.

The following changes have been incorporated:

- The imputation rule for missing scores in ITSQ is updated in section 5.2.10.1.
- The analysis of nonnocturnal hypoglycemia and pseudo hypoglycemia is deleted.
- Subgroup analysis of entry age (<75 , ≥ 75) and entry HbA_{1c} levels ($<7\%$, $\geq 7\%$) are deleted. BMI cut point changed from 28, 30 to 24, 28
- One more rule added to exclude subjects from Per Protocol Set: Missing HbA_{1c} at baseline and/or at primary endpoint (week 24; only for subjects who should have V18)
- The definition of TEAR is updated.
- The shift tables of total insulin antibody and cross reactive insulin antibody are deleted.
- The analysis concerning to the following hypoglycemic categories were deleted:
 - Severe hypoglycemia (BG level ≤ 70 mg/dL[3.9 mmol/L])
 - Severe hypoglycemia (not biochemically confirmed—BG missing)
 - Severe hypoglycemia (not biochemically confirmed—BG not aligned with severe symptoms)
 - Nonnocturnal hypoglycemia
 - Pseudo-hypoglycemia

4. Study Objectives

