5.2. Statistical and Analytical Plans

5.2.1. General Considerations

All data will be entered, verified, and archived by a contract research organization (CRO) external to Lilly and/or at Lilly. Data listings, summaries, and analyses will be performed by a CRO and/or by Lilly under the guidance and approval of statisticians at Lilly. Statistical analysis of this study will be the responsibility of Lilly.

Any change to the data-analysis methods described in the protocol will require an amendment ONLY if it changes a principal feature of the protocol. Any other change to the data analysis methods described in the protocol, and the justification for making the change, will be described in the statistical analysis plan and/or in the clinical study report (CSR). Additional exploratory analyses will be conducted as deemed appropriate.

The patient populations used in the study are described below:

1. All Patients Entered - all patients who signed ICF
2. All Randomized - all patients who were randomized to a treatment arm
3. Full Analysis Set (FAS) - based on the intent to treat (ITT) principle, all patients who were randomized and who have taken at least one dose of study medication will be included in this analysis set. Patients will be analyzed according to the treatments to which they were randomized.
4. Per-protocol (PP) - patients in the FAS/ITT population who also meet the criteria in Trial Issue Management Plan (TIMP), and treatment group will be defined on the basis of the treatment the patients actually receive:
 - a. have no violations of Inclusion/Exclusion Criteria specified in TIMP
 - b. have not discontinued from the study prior to 24 weeks
 - c. have not been off study medication for more than 14 consecutive days during the treatment period

- d. have not received chronic (lasting longer than 14 consecutive days) systemic glucocorticoid therapy (excluding topical, intra-articular, intraocular, and inhaled preparations)
- e. Missing HbA1c at baseline and/or at primary endpoint (week 24; only for subjects who should have V18)

Unless otherwise specified, listings will be prepared using all randomized patients. Efficacy and safety analyses will be conducted using the FAS population. Selected analyses will be conducted using the All Randomized population and the PP population.

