5.2.12. Subgroup Analyses

The consistency of the treatment effect for the change in HbA_{1c} level will be assessed within subgroups in the FAS population if there are sufficient numbers of patients in each subgroup (e.g. 20 patients per cell). The following subgroups will be analyzed:

- Entry HbA_{1c} levels (<8.5%, ≥8.5%)
- Entry BMI (<28, ≥28)
- Entry BMI (<24, ≥24)
- Entry age (<65, ≥65)
- Gender
- Entry use of insulin secretagogues (SU, meglitinide, neither)
- Renal function, as estimated by estimated glomerular filtration rate (EGFR) using the MDRD formula (see [Appendix 2](#)). The following EGFR categories will be used:
 - Normal or increased GFR: EGFR (≥90 mL/min/1.73 m²)
 - Mild reduction in GFR: EGFR (60-89 mL/min/1.73 m²)
 - Moderate reduction in GFR: EGFR (30-59 mL/min/1.73 m²)
 - Severe reduction in GFR: EGFR (15-29 mL/min/1.73 m²)
 - Kidney failure: EGFR (<15 mL/min/1.73 m²).

The categories of severe reduction in GFR and kidney failure will be combined if there are fewer than 20 patients in either of these categories.

The change in HbA_{1c} from baseline to 24-week endpoint will be analyzed using MMRM with treatment (LY2963016, Lantus®), entry use of insulin secretagogue (SU, meglitinide, neither), visit, subgroup, subgroup-by-treatment interaction, subgroup-by-visit interaction, treatment-by-visit interaction, and treatment-by-visit-by-subgroup interaction as fixed-effects; the baseline value of HbA_{1c} as a covariate, and a random effect for patient for the FAS. If the subgroup is one of the stratification variables, then the subgroup will only be included once in the model. A significant treatment-by-subgroup interaction (p<.05) may be indicative of a differential treatment effect across levels of the subgroup, necessitating further exploration of the nature of the interaction.

For each subgroup listed above, the change in weight from baseline to 24-week will be analyzed using the same methodology as the subgroup analysis of HbA_{1c}, except baseline weight will be added as another covariate.

Additional subgroup analyses will be carried out on selected safety outcomes:

- a) total or nocturnal hypoglycemia at 24-week endpoint and for the overall 24-week period (rates and incidence)
- b) treatment-emergent antibody response (TEAR) at 24-week endpoint and for the overall 24-week period
- c) detectable insulin antibodies at 24-week endpoint and for the overall 24-week period
- d) categories of adverse events:

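### Adding a baseline HbA1c-by-visit term to the primary MMRM and its per-protocol repeat is a cheap improvement; the model as written is valid, and the term helps only if the baseline slope changes between week 4 and week 24

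*SAP*

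**What the plan says.** SAP 5.2.7 specifies a likelihood-based MMRM on the FAS under missing at random, with unstructured covariance. Its terms are treatment, entry secretagogue use, "visit, and interaction between visit and treatment as fixed effects; the baseline value of HbA_{1c} as a covariate". Protocol 12.2.6 has the same structure: "visit, and interaction between visit and treatment as fixed effects; the baseline value of HbA1c as a covariate; and a random effect for patient". HbA1c is measured after baseline at weeks 4, 8, 12, 16, 20 and 24.

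The week-24 interval from this model is compared with +0.4% and, if that test passes, with −0.4%. For the per-protocol set, SAP 5.2.7 states: "A first secondary analysis of the primary efficacy outcome will use the same MMRM model described above with the PP patient population". The other supportive analysis, an ANCOVA on the FAS, has its own endpoint slope but carries the last observation forward. No analysis adds a baseline-by-visit term.

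Three other places bear on the point:
- Protocol 7.2.1 expects most titration to be finished by week 12.
- Protocol 8.3.3 gives, as one example of discontinuation for lack of efficacy at the investigator's discretion, a patient at the fasting target whose "HbA1c levels remain above 8.0% on at least 2 consecutive occasions in the absence of any signs of continued improvement".
- The subgroup MMRM in SAP 5.2.12 includes "visit, subgroup, subgroup-by-treatment interaction, subgroup-by-visit interaction, treatment-by-visit interaction", and entry HbA1c split at 8.5% is one of its subgroups.

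**The concern.** A single slope assumes that a patient's starting HbA1c predicts the change at week 4 as strongly as at week 24. In a titration trial the early visits record a response still in progress, so the slope may steepen with time. If it does, the fitted common slope is pulled toward the early visits, where HbA1c change is less variable, and week 24 is adjusted too little for baseline.

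This would have two consequences:
- **Precision.** Baseline variation that the model could have explained stays in the week-24 residual, so the interval is somewhat wider than it need be.
- **Bias, under a further condition.** If patients leave in a way that depends on baseline differently by arm, those remaining differ in baseline, and a slope that is too shallow leaves part of that gap in the treatment comparison.

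Both noninferiority decisions rest on this one interval.

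**Working it through.** **1. The plan's own figure.** Inputs from SAP 5.1: margin 0.40, SD 1.3, true difference 0, 450 completers at 2:1 (300 and 150), two-sided 0.05, 15% dropout.

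- SE = 1.3 × √(1/300 + 1/150) = 0.130.
- Power = Φ(0.40/0.130 − 1.96) = Φ(1.117) = 86.8%, which agrees with over 85%.
- 450/0.85 = 529.4, so 530 randomised.

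**2. Large-sample effect of a common slope.** Let s be the six visit-specific slopes, S the residual covariance, S24 its week-24 variance and SDb the baseline SD.

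- Fitted common slope: b = (1′S⁻¹s)/(1′S⁻¹1).
- Week-24 interval width, common slope relative to by-visit: √(1 + SDb²(s24 − b)²/S24).
- Shift in the estimate ≈ |s24 − b| × the baseline gap left between arms.

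The documents give no slopes, baseline SD or visit correlations. Those below are assumptions; only the week-24 SD of 1.3 is stated. Worked case: SDb 0.93; residual correlation 0.8 between adjacent visits, decaying with distance; SD 0.8 at week 4 rising to 1.3 at week 12; slope reaching −0.6 at week 16. Then S24 = 1.69 − (0.6 × 0.93)² = 1.379.

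| Week-4 slope | −0.4 | −0.3 | −0.2 |
|---|---|---|---|
| Common slope b | −0.425 | −0.350 | −0.278 |
| Shortfall at week 24 | 0.175 | 0.250 | 0.322 |
| Extra interval width | 0.95% | 1.9% | 3.2% |
| Shift for a 0.10 baseline gap | 0.018 | 0.025 | 0.032 |

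For example, √(1 + 0.8649 × 0.0625/1.379) = 1.019.

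Over 540 assumed settings per step, the median extra width was 0.9%, 1.8% and 3.0% for steepening of 0.2, 0.3 and 0.4. The full range was 0.1–12.5%. With a constant slope it is 0%.

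**3. Simulation at trial size, same dropout rule in both arms** (530 randomised, about 16% dropout, week-24 slope −0.6, 4,000 runs, secretagogue term omitted).

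| Week-4 slope | −0.6 (constant) | −0.4 | −0.3 | −0.2 |
|---|---|---|---|---|
| SE as written | 0.1148 | 0.1158 | 0.1170 | 0.1184 |
| SE with the term | 0.1148 | 0.1148 | 0.1149 | 0.1150 |
| Extra width as written | 0% | 0.9% | 1.8% | 3.0% |
| Equivalent completers of 450 | 0 | 8 | 16 | 26 |
| Primary power, as written / with term | 94.4 / 94.4% | 93.1 / 93.2% | 93.0 / 93.6% | 92.1 / 93.2% |
| Both tests passed, as written / with term | 88.5 / 88.5% | 86.6 / 86.9% | 85.6 / 87.0% | 84.5 / 86.4% |

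Equivalent completers are 450 − 450/(1 + w)², with w the extra width. False noninferiority at a true difference of 0.4 was 2.05–2.55% as written and 2.4–2.75% with the term, against a nominal 2.5%. The stated 85% refers to the primary test only.

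**4. Dropout depending on baseline in opposite directions by arm** (log-odds 0.5 per 1% HbA1c, about 14% dropout, completer baseline gap 0.12, reference arm losing high-baseline patients).

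| Week-4 slope | −0.6 | −0.4 | −0.3 | −0.2 |
|---|---|---|---|---|
| FAS bias as written | 0 | −0.014 | −0.020 | −0.019 |
| PP bias as written | 0 | −0.022 | −0.030 | −0.033 |
| FAS false noninferiority as written | 2.8% | 3.3% | 3.7% | 3.6% |

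With the term, FAS bias is at most 0.005 in size and false noninferiority is 2.6–2.7%. Dependence in one arm only gave a FAS bias of −0.009 to −0.012. Reversing the arms gave +0.008 to +0.021, against LY2963016 (1,500 runs). Monte Carlo error in the 4,000-run settings is about 0.25 points on error rates and 0.002 on bias.

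**5. Range under stronger assumptions.** A separate simulation that kept the secretagogue term used slope changes of 0.35 and 0.58. It gave an SE 2–10% smaller with the term, and a common-slope bias of about 0.03 and 0.05 at log-odds ±0.5. A stress test at ±1 gave about 0.06 and 0.10. With flat slopes the SE ratio was 1.001.

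**The case against.** The strongest reply is that nothing here is an error. Protocol and SAP agree, the model is a recognised one, and with a common dropout rule it is valid and if anything slightly conservative. Its simulated SE of 0.115–0.118 is below the planning SE of 0.130. All of this stands. A reader might infer that the interval is wider than planned; it is wider only than the same model with the extra term.

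A reader might also take the discontinuation example in Protocol 8.3.3 as evidence of bias. It is not. It describes one rule for both arms, driven by on-study HbA1c that the likelihood analysis uses. Simulating that rule in a large sample, with week-4 slopes of −0.4 and −0.2, gave these differences between the common-slope and by-visit estimates:
- same rule in both arms: within 0.002;
- rule applied over twice as often in the reference arm: −0.005 and −0.013;
- rule never applied in one arm: −0.010 and −0.025.

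Open-label treatment makes uneven application possible. No passage supports dropout that depends on baseline in opposite directions.

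Nor is the subgroup model an inconsistency. Its subgroup-by-visit term is the lower-order term that its three-way interaction requires, and it does not show that the sponsor expects the baseline effect to vary.

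Finally, the sizes rest on assumed slopes, and the change would come late: the SAP already plans COVID-19 listings, while the protocol estimates the last visit for February 2020. That argues for careful documentation. It does not remove the case for the term, since the only analysis with a separate endpoint slope also switches to LOCF and so cannot isolate this assumption.

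**Conclusion.** This is a cheap improvement of minor severity, held with medium confidence. It does not correct an invalid analysis. The result depends on conditions that the documents leave open:

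- **Constant baseline slope:** no gain and no bias.
- **Slope steepening by an assumed 0.2–0.4:** the week-24 interval is typically about 1–3% wider than it need be, and primary power remains above 85%.
- **Changing slope and dropout that depends on baseline differently by arm:** a bias of about 0.01–0.03 HbA1c points, at most about 8% of the margin (0.03/0.4 = 7.5%), in either direction. Larger figures need steeper slopes or the stress-test dropout.

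A reader might conclude that the noninferiority decision is biased toward LY2963016, or that the term is certain to add precision. The documents support neither reading: they report no slopes, and nothing in them shows that arm-differential dropout on baseline will occur.

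**What to change.** In SAP 5.2.7 and Protocol 12.2.6, add baseline HbA1c-by-visit as a fixed effect in the primary HbA1c MMRM, and so in its per-protocol repeat. Report the model as now written as a sensitivity analysis. No change is proposed to the other models.

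Timing should follow the SAP's Revision History: "Version 2 of the SAP will be approved prior to the first unblinding of the clinical team and prior to the database lock". The sponsor must first decide whether this changes a principal feature of the protocol, which would need an amendment. If not, SAP 5.2.1 applies: "Any other change to the data analysis methods described in the protocol, and the justification for making the change, will be described".

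The statistical cost is five fixed-effect degrees of freedom (six slopes in place of one), about 0.1% of the SE or less if slopes are constant. No new data are needed, and there is one extra sensitivity run. The real cost is procedural: this alters the primary model of an open-label trial in a direction that usually narrows the interval, so the reason must be on record before anyone sees results by arm. If the sponsor prefers to leave the primary model alone, prespecifying the by-visit version as the sensitivity analysis would still show whether the assumption matters.
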